2.3.14. Statistical methods

2.3.14.1. Statistical method for primary and secondary outcomes

Primary outcome: proportion of medication errors

The proportion of medication errors is the proportion of paramedics committing a medication error. For each type of medication (epinephrine, midazolam, dextrose 10%, sodium bicarbonate), the proportion of medication errors will be reported with 95% confidence intervals (CI, Clopper-Pearson's method) when PedAMINES is used and when the conventional preparation method is used. The difference in proportion of medication errors between preparation methods will also be reported with 95% CI (exact method). The association between the preparation methods (PedAMINES versus conventional method) and the risk of error will be assessed by using a logistic regression model with mixed effects to account for the repetition of measures among paramedics. A random intercept will be introduced in the model. The model will be adjusted for the type of medication since the risk of error can vary across medications.

Secondary outcomes:

a) Proportion of other errors:

The proportions for other types of errors (the choice of drug, air purge in the syringe, labeling of the filled syringe, aseptic errors) will be analyzed in a similar manner as for the primary outcome.

b) Deviation from the correct weight-based dose:

For each of the 4 drugs prepared, errors will be measured by the deviation from the amount of drug taken, the amount of saline solution taken to dilute the drug, the final concentration and the correct weight-based dose. Absolute deviation will be analyzed for each type of medication. The mean (or median) difference in deviation obtained with PedAMINES and with the conventional preparation method will be reported with 95% CI (or inter-quartile interval). A t-test or a Mann-Whitney's test will be used for comparing preparation methods.

c) Time to drug preparation (TDP) and delivery (TDD):

For TDD and TDP, the mean times will be reported with 95% CI for each preparation methods and for each type of medication. The mean difference between preparation methods will also be reported with 95% CI. The association between the preparation methods and TDP and TDD will be assessed by using a linear regression model with mixed effects to account for the repetition of measures among paramedics. A random intercept will be introduced in the model. The model will be adjusted for the type of medication since TDP and TDD can vary across medications.

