2.3.3. Study design

The study is a prospective, multicenter, randomized controlled trial with 2 parallel groups comparing PedAMINES^{46,47} with conventional precalculated drug dosing charts used by EMS in the preparation of direct IV drugs during a standardized simulation-based pediatric cardiac arrest scenario. The drug dosing charts is presented as a spreadsheet, enabling the preparation of the commonly ordered concentrations of emergency medications at varying dose ranges based on the patient's weight. To calculate the composition of the drug to inject, one first selects the desired drug dosage to be delivered in mg/kg. The next step is to calculate the milliliters of drug based on the weight of the patient to be diluted with compatible fluids (sodium chloride 0.9%, etc) in a syringe. For the purpose of the study, we will not select drugs that can be directly drawn from the vial without calculation and dilution.

The multicentric setting of the study will involve 15 Swiss EMS (Cantons of Geneva, Vaud, Neuchâtel, Fribourg, Jura, Zurich, Bern, Basel, Lucern, Ticino). To ensure optimal quality of reporting, the trial is formatted according to the Consolidated Standards of Reporting Trials Statement for Randomized Controlled Trials of Electronic and Mobile Health Applications and Online TeleHealth (CONSORT-EHEALTH)⁴⁸ and the Reporting Guidelines for Health Care Simulation Research⁴⁹

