2.3.5.4. Concomitant care

The paramedics will be allowed to use their current, conventional method of preparing direct IV drugs, even if it differs between EMS. This will avoid introducing evaluation bias on the baseline ability of paramedic to prepare drugs “as usual” if allocated in the group without PedAMINES. This will also test the absolute capacity of the app to reduce medication errors and drugs delays, indifferently of the prior traditional method used.

However, participants will not be allowed to use any other drug support device and the scenario will remain secret until it starts to avoid upstream drugs preparation's refresh.

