2.3.8. Sample size

The primary objective of this study is to detect a difference in proportions of medication errors between groups (with PedAMINES vs without PedAMINES). The expected proportion of errors made without PedAMINES is 60%¹¹. We consider that a difference of 30% in the proportion of medication errors is sufficient to modify the practice. Therefore, the sample size was calculated to reach a statistical power of 90% in detecting an absolute difference of at least 30% in proportions of medication errors between intervention groups. With a two-sided risk alpha of 0.05, the needed sample size is 56 paramedics per arm of the study. To prevent a potential loss of power due to misspecification of assumptions, 60 paramedics will be recruited per randomized group (total sample size: 120 paramedics).

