2.3.10. Assignment of intervention

2.3.10.1. Allocation sequence

A single randomization of the participants (paramedics) will be done using an online computing web randomisation service⁵⁵ to generate the randomisation list. With this method, paramedics will be randomly assigned to either group A (using PedAMINES) or to group B (conventional preparation methods) with a single, constant 1:1 allocation ratio. One randomization list per EMS center will be produced (randomization stratified on center) and block of random size will be used to generate the randomization lists.

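### Randomization is stratified by EMS, but none of the main analyses includes EMS, so the precision gained by stratifying is not reported if EMS shifts both arms' outcomes.

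*Combined protocol and SAP*

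**What the plan says.** - **Design.** Section 2.3.3 states: "The multicentric setting of the study will involve 15 Swiss EMS". Section 2.3.10.1 states: "One randomization list per EMS center will be produced (randomization stratified on center", with blocks of random size, "with a single, constant 1:1 allocation ratio".
- **Primary outcome and other errors (2.3.14.1).** A logistic mixed model with preparation method, drug and a random intercept. The intercept is there for the repeated measures within a paramedic, so it is not an EMS term. On covariates: "The model will be adjusted for the type of medication since the risk of error can vary across medications".
- **TDP and TDD (2.3.14.1).** The linear counterpart: "The model will be adjusted for the type of medication since TDP and TDD can vary across medications".
- **Dose deviation (2.3.14.1).** "A t-test or a Mann-Whitney's test will be used for comparing preparation methods", with no stratification.
- **Additional analyses (2.3.14.2).** An urban/rural interaction and a correlation with EMS call exposure. Neither puts the 15-level stratum into the main comparison.
- **Control condition (2.3.5.4).** "The paramedics will be allowed to use their current, conventional method of preparing direct IV drugs, even if it differs between EMS".

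**The concern.** Stratifying by EMS forces near-equal arm sizes within each EMS, so differences between EMS largely cancel out of the arm comparison. An analysis without EMS does not recognize this. The paramedic intercept does not help: it absorbs EMS variation into between-paramedic variance, and that variance feeds the standard error of a comparison made between paramedics.

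The plan adjusts for drug because risk differs between drugs. The same reasoning applies to the factor on which it chose to stratify. At stake are confidence intervals wider than the design warrants and tests that reject less often than stated. This matters most for TDP, TDD and dose deviation, for which section 2.3.8 gives no power calculation.

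There is a second, separate mechanism. Section 2.3.5.4 permits, without asserting, conventional methods that differ between EMS. Such differences act only in the control arm. That is an EMS-by-treatment interaction, which no main model addresses.

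**Working it through.** **Inputs from the documents.** 15 EMS (2.3.3); 120 paramedics, 60 per arm; 60% errors in the control arm and a 30-point difference; two-sided alpha 0.05 and 90% power (2.3.8); four drugs per paramedic. An even spread gives 120/15 = 8 paramedics per EMS, about 4 per arm.

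**Assumed, because the documents do not give it.** rho, the EMS share of paramedic-level variance, taken as 0.02 to 0.20.

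**1. The plan's own figure.** Section 2.3.8 says "the needed sample size is 56 paramedics per arm of the study". With pooled variance and no continuity correction:

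n = [1.96·√(2·0.45·0.55) + 1.2816·√(0.6·0.4 + 0.3·0.7)]² / 0.3² = (1.379 + 0.860)² / 0.09 = 55.7, rounded up to 56.

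This reproduces the plan. Power is 90.2% at 56 per arm and 92% at 60, without any EMS term.

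**2. EMS shifts both arms alike.** The true variance of the arm difference is (1 − rho) times the variance that the unadjusted analysis reports. So:

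- ratio of reported to true SE = 1/√(1 − rho)
- actual alpha = 2·[1 − Φ(1.96/√(1 − rho))]
- equivalent sample size when EMS is included = 120/(1 − rho)

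| rho | SE too large by | actual alpha | equivalent N |
|---|---|---|---|
| 0.02 | 1.0% | 0.048 | 122 |
| 0.10 | 5.4% | 0.039 | 133 |
| 0.20 | 11.8% | 0.028 | 150 |

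**3. Binary errors, four drugs per paramedic.** Simulation of 15 EMS × 8 paramedics × 4 drugs, paramedic SD 1 logit, analysed on paramedic means, 6,000 runs per scenario, 60% errors in both arms for the null:

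| EMS SD (logit) | SE ratio | null rejection without EMS | with EMS |
|---|---|---|---|
| 0.3 | 1.02 | 4.3% | 4.7% |
| 0.5 | 1.05 | 3.9% | 4.8% |
| 1.0 | 1.17 | 2.2% | 5.3% |

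An SE ratio of 1.05 corresponds to rho = 1 − 1/1.05² ≈ 0.09, so an EMS SD of 0.5 lies near the middle row of the first table. With 60% and 30% read as error rates per preparation (an assumption), power exceeds 99.9% with or without EMS.

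The planned type of mixed logistic model was also fitted with and without an EMS intercept (EMS SD 0.5, log-odds effect −0.85, 700 runs). Type I error was 3.7% without and 4.7% with EMS; power was 83.4% and 85.9%.

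**4. Dose deviation.** Log-normal deviations, t-tests on the log scale, 8,000 runs per rho, null rejection at rho 0.10 and 0.20:

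- t-test: 3.8% and 2.9% without EMS; 4.7% and 4.8% with EMS.
- Mann-Whitney: 3.8% and 3.0%; EMS-stratified rank test: 4.2% and 4.6%.

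**5. EMS varies only in the control arm.** Same setting as step 3, null case. If the 15 EMS are treated as a sample of a wider population, type I error is:

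| control-arm EMS SD (logit) | no EMS term | EMS main effect | EMS-by-treatment variation used |
|---|---|---|---|
| 0.5 | 6.9% | 7.1% | 5.5% |
| 1.0 | 10.8% | 11.9% | 5.1% |

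At SD 1.0 the true SD of the estimate is 0.068, against a reported SE of 0.055 without EMS and 0.053 with an EMS main effect. If the inference is only to these 15 EMS, the true SD is 0.050 and the planned SE of 0.055 is again conservative.

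**6. No EMS variation.** In the paramedic-mean analysis the mean SE is 0.0524 with and without EMS.

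**The case against.** The strongest reply is that no conclusion changes. The estimate is unbiased, the stated power holds, and at small rho the interval is about 1% too wide. The size rests on an assumed rho, and the fixed manikin, scenario and study team limit variation between sites. Eight paramedics per EMS is only an average, and random block sizes balance small strata only approximately. All of this stands, and it is why the point is one of efficiency and not of validity.

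It is also fair that the estimate does not improve when EMS is added to a balanced design. In a mixed logistic fit (EMS SD 0.5, 200 runs) the empirical SD was 0.299 either way, and only the reported SE moved, from 0.293 to 0.280. At error rates near those of the earlier in-hospital crossover trial (75.9% versus 10.2%, section 2.2) it moved from 0.446 to 0.436, about 2%. So the loss lies in reported uncertainty and error rate.

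The most serious objection is that the one mechanism with direct textual support, differing conventional methods, acts in the control arm, where an EMS intercept does not help and slightly raises type I error (step 5). This also stands. It is a reason to add the interaction sensitivity model, not to leave the stratification factor out. EMS may differ in both arms too: the summary refers to differing EMS competencies, and section 2.3.14.2 tests for urban/rural differences.

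**Conclusion.** The concern holds. The main analyses do not follow the randomization. With an EMS effect common to both arms, the reported standard error is too large by 1.0% to 11.8% for rho from 0.02 to 0.20, and the nominal 5% test runs at 4.8% down to 2.8%. There is no bias and no inflated false-positive rate in that case, and the 56 per arm is sound. With rho near zero the consequence is negligible.

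The direction reverses only if EMS differences sit in the control arm and the results are read as applying beyond the 15 EMS. Type I error is then about 7% at an assumed SD of 0.5 logit and 11% at 1.0. The plan does not state the target of inference. This should be corrected before analysis, but it does not undermine the trial.

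**What to change.** - **Mixed models.** Add an EMS random intercept, with paramedic nested in EMS, to the logistic models for the primary outcome and other errors and to the linear models for TDP and TDD. State in advance that if the EMS variance is estimated as zero the result is reported as it stands. This will not be rare: in trial fits it happened in 15–20% of runs at EMS SD 0.5 and 63% at SD 0.
- **Dose deviation.** Use a linear comparison adjusted for EMS or, if rank-based, a van Elteren test stratified by EMS.
- **Drug-specific proportions.** Keep the planned Clopper-Pearson and exact intervals as descriptive. An EMS-stratified risk difference is optional.
- **Target of inference.** Say whether conclusions concern these 15 EMS or a wider population, and add a sensitivity analysis with an EMS-by-treatment term.

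The cost is one model term, a stratified version of one test, one sensitivity model and some wording. It needs no further data or participants.

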PedAMINES is much more than just a calculator. The app lists all the available resuscitation drugs, either for direct IV or continuous infusion, with doses automatically adapted to the weight or age of the patient entered when starting the app. The list can be expanded and customized according to users' need and to local drugs habits internationally. Drugs (concentration, volume, etc.) are fully editable to adjust for each center internationally. Safety of the app (doses, calculations, etc.) is guaranteed both by the calculation algorithm created and checked by the developers' team and by the data edited by each user. By a simple touch, any of the listed drugs can be selected and the exact amount to prepare is clearly displayed making calculations useless (Figure 2). This is based on the app's ability to automatically calculate the optimal weight-based drug dose, independently of the user competency in this domain. Multiple drugs can be prepared and run in parallel. All actions performed are stored locally on the device in historic files to preserve information that can be retrieved at any time for debriefing or medicolegal purposes. Historic files can also be erased or safely exported and saved in electronic health records. PedAMINES is so simple to use and powerful that even inexperienced users may use it after a 5-minutes training session. This was particularly obvious in our SNSF granted study where distribution of individual delays was less spread with PedAMINES than with the conventional method (Figure 1). This suggests a worthwhile benefit to its use in the prehospital setting where paramedics are infrequently exposed to pediatric CPR but have to use resuscitative drugs before to transfer the patient to a tertiary care center.

Fig 2. PedAMINES application screenshot

Need for a trial: To our knowledge, PedAMINES is the first scientifically validated app to improve drug preparation during in-hospital pediatric CPR and able to sustain cognitively users during this process. However, a big challenge remains. To date, very few pediatric studies of medication errors and error prevention strategies have been performed in

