2.3.2. Objectives and hypothesis

We aim to determine whether the prehospital use of PedAMINES by EMS in Switzerland reduces medication errors, as well as TDP and TDD.

Research hypothesis: Herein, we hypothesize that PedAMINES reduces medication errors and TDP and TDD independently of existing conventional preparation methods (i.e. precalculated drug dosing charts) or EMS' skills.

Primary objective: To determine whether prehospital use of PedAMINES during pediatric resuscitation reduces medication preparation errors compared with conventional methods.

Secondary objective: To determine whether prehospital use of PedAMINES during pediatric resuscitation reduces dosing deviations and other types of errors (see below) compared with conventional methods. To determine if PedAMINES leads to a shorter time in direct IV drugs preparation (TDP) and delivery (TDD).

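### The dosing-deviation outcome is compared drug by drug, with no lead measure and no estimate across the four drugs, although the plan pools the drugs for errors and times

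*Combined protocol and SAP*

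**What the plan says.** Section 2.3.2 sets as a secondary objective to find out whether the app "reduces dosing deviations and other types of errors (see below) compared with conventional methods".

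Section 2.3.14.1 b) gives the only between-arm analysis of deviation. It begins "For each of the 4 drugs prepared, errors will be measured by the deviation from the amount of drug taken" and continues with "the amount of saline solution taken to dilute the drug, the final concentration and the correct weight-based dose". That makes four measures. It then states "Absolute deviation will be analyzed for each type of medication", reports a mean or median difference between methods, and compares the methods by a t-test or a Mann-Whitney test. It contains no model, drug term, lead measure or multiplicity rule.

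The neighbouring outcomes are treated differently:

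- **Dosing errors (primary):** a mixed logistic model over the four drugs, with a random intercept and adjustment for drug.
- **Other errors, a):** handled like the primary outcome.
- **TDP and TDD, c):** a "linear regression model with mixed effects to account for the repetition of measures among paramedics", again with a random intercept and adjustment for drug.

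Section 2.3.14.2 adds subgroup and interaction analyses but no pooled estimate of deviation.

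**The concern.** Each paramedic prepares all four drugs, so deviation has the same repeated-measures structure as errors and times. The plan uses that structure for every other preparation outcome and drops it for this one without giving a reason.

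Two things follow. First, the report will contain a set of drug-specific results and no single figure for how much the app reduces dose deviation overall. With no lead measure, attention may settle on whichever result happens to be significant. Second, each comparison uses one preparation per paramedic where four are available, so precision is lost on data already collected. Section 2.3.5.1 has the delivered amount measured from the syringe and the video.

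The term absolute deviation is also undefined: it could mean an unsigned value or a value in raw units (mL, mg/mL). Raw units cannot be averaged across drugs.

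**Working it through.** **Inputs from the documents.** Four drugs and four deviation measures (2.3.14.1); two-sided alpha 0.05, 60% versus 30% errors, 90% power, 56 per arm needed and 60 recruited (2.3.8). The documents give no correlation, variance or effect size for deviations; those used below are assumptions.

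**The plan's own figure.** With mean proportion 0.45, n = [1.960 × √(2 × 0.45 × 0.55) + 1.282 × √(0.6 × 0.4 + 0.3 × 0.7)]² / 0.30² = (1.379 + 0.860)² / 0.09 = 55.7, so 56 per arm. The stated figure is reproduced. It concerns the primary outcome and does not depend on this point.

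**Number of tests.** On the wide reading, every listed measure is tested for every drug: 4 × 4 = 16. On the narrow reading, suggested by the title of section b), only deviation from the weight-based dose is tested: 4 × 1 = 4. The text does not settle which is meant.

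**Chance of at least one false positive, no true effect, each test at 5%.**

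- 16 independent tests: 1 − 0.95^16 = 0.560. Expected number of false positives: 16 × 0.05 = 0.8.
- 4 independent tests: 1 − 0.95^4 = 0.185.
- Positive correlation lowers both. Simulation of equicorrelated normal test statistics (200,000 replicates) gave:

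| Assumed common correlation | 16 tests | 4 tests |
|---|---|---|
| 0.3 | 48% | 17% |
| 0.5 | 38% | 16% |
| 0.8 | 21% | 11% |

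Concentration and dose follow largely from the two volumes, so measures within a drug must be correlated and 56% is a ceiling.

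**Precision from pooling.** With equal variances and intra-paramedic correlation ρ, the mean of four preparations has variance (1 + 3ρ)/4 times that of one, so the ratio of standard errors is √((1 + 3ρ)/4):

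- ρ = 0.3: √0.475 = 0.689
- ρ = 0.5: √0.625 = 0.791
- ρ = 0.8: √0.85 = 0.922

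**What that means at 60 per arm.** The standardised difference detectable with 80% power in one drug is (1.960 + 0.842) × √(2/60) = 0.511. Pooled, it is 0.511 × 0.791 = 0.404 at ρ = 0.5. For an assumed difference of 0.4 that is common to all drugs, power is 59% for one drug, against 89% (ρ = 0.3), 79% (ρ = 0.5) or 66% (ρ = 0.8) pooled (normal approximation).

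**Why the pooled measure must be unsigned.** Suppose half the doses in an arm are twice the correct dose and half are half of it. The mean signed log-ratio is (log 2 + log 0.5)/2 = 0, the same as for perfect dosing. The mean unsigned percentage deviation is (100 + 50)/2 = 75%. A signed log-ratio is also undefined for a zero dose.

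**The case against.** The best defence is that the plan already has a pooled answer on dosing accuracy. Section 2.3.6 defines the primary outcome as a deviation of more than 10% from the correct dose, and the primary model pools it over the four drugs. Each per-drug comparison of dose deviation also bears directly on the objective. This stands: a reader might infer that no planned test addresses the objective, and that would be wrong. What is missing is a pooled estimate on the continuous scale.

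It is also fair that these are secondary outcomes with no confirmatory claim, and that the false-positive figures assume no effect on any measure. The earlier in-hospital studies in section 2.2 report large reductions in errors. The 16 tests are derived, not printed. A reader should take neither 16 as stated nor 56% as the actual error rate.

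A reader might further infer that raw mL or mg/mL deviations mean different things at different EMS, so that one service with a weak solution dominates the mean. Section 2.3.5.4 does allow the conventional method "even if it differs between EMS", and section 2.2 says of the app "Drugs (concentration, volume, etc.) are fully editable to adjust for each center internationally". The first concerns the preparation method and the second describes an app feature. Neither states that stock concentrations differ between the participating EMS. Randomisation stratified by EMS would roughly balance any such difference between arms, leaving added variance and no systematic bias. The point does not depend on this.

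Lastly, analysis by drug is defensible because preparations and units differ, and a single pooled effect assumes a common effect across drugs. That is a reason to keep the per-drug results alongside a pooled one.

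**Conclusion.** The gap is real but modest. Section b) has no lead deviation measure and no estimate across drugs, while the plan's own method for errors and times would supply one at little cost.

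The number of between-arm tests is 16 or 4, depending on how the section is read. The matching chance of at least one false positive under no effect is at most 56% (about 21% to 48% at assumed common correlations of 0.8 to 0.3) or 18.5% under independence. The precision forgone corresponds to a pooled standard error of about 69% to 79% of a single-drug one at an assumed correlation of 0.3 to 0.5. The gain shrinks to 92% at 0.8. These ratios assume equal variances and exchangeable correlation across drugs; the power figures also assume a common effect.

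The primary analysis and the sample size are not touched. Nor does the point require dropping the per-drug p-values; that would be a matter of preference.

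**What to change.** In section 2.3.14.1 b), before the data are analysed:

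1. Name one lead deviation measure: the unsigned percentage deviation of the delivered dose from the correct weight-based dose. This is the relative scale that the primary outcome already uses, and it settles what absolute means.
2. Analyse it over all four drugs with a linear mixed model as in section c): arm, drug, and a random intercept per paramedic, giving one between-arm estimate.
3. Because values may be skewed and may pile up near zero, use a transformation defined both at zero deviation and at zero dose, such as log(1 + |percentage deviation|), with a robust or bootstrap 95% CI. A zero dose is then a deviation of 100% and stays in the analysis.
4. State in advance how preparations of the wrong drug, which section 2.3.6 A records, enter this measure.
5. Keep the per-drug comparisons and the mL and mg/mL measures as supportive, and say which of them will be tested.

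The cost is wording and one extra model on data already collected. The small downside is that the pooled estimate assumes a common effect across drugs, which is why the per-drug results should be shown beside it.

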On the day of participation, paramedics will complete a survey collecting data regarding their demographics, care training, and simulation and computer experience. After random allocation, each participating paramedic will receive a standardized 5-minute training session on how to use the PedAMINES app. Paramedics will remain unaware of drugs that will be used and specific endpoints of the study during this training session. The simulation manikin characteristics are then presented. The paramedics will then be asked to perform the pediatric resuscitation scenario. This scenario is standardized to follow the same chronological progression and range of difficulty to ensure each participant is exposed to exactly the same case, with similar challenges in decision making and treatment preparation provided on the same manikin. The uniform delivery of the scenario all along the study will minimize confounders. Study team members will only adapt to progression speed of participants through the scenario by maintaining a stressful resuscitation atmosphere. The scenario will be videorecorded and conducted in a simulated children room in each area in order to increase realism. High levels of realism are known to immerse participants in the simulated experience and prevent confounding

variables that might potentially affect the way individuals perform⁵⁰. The simulated room will be exclusively devoted to the simulation to prevent unexpected interruption or external stimuli. Portable monitoring alarms will be activated to increase realism and stress. All usual EMS resuscitation equipment will be at the disposal of the paramedic. In both allocation groups, the decision to use or not use any equipment will remain personal as in real life. Neither pilot testing nor repetitions will be permitted. There will be neither interventions nor educational adjuncts prior to or after the study period. Once the experiment completed, the paramedic will be required to recall and describe precisely how he prepared the drugs in order to verify that the drug names and original doses prescribed by the physician were correctly understood to assess the presence of comprehension bias.

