2.3.14.2. Statistical methods for additional analysis

For the primary and secondary outcomes, logistic regression analyses will be conducted to test a difference in rates of errors between urban EMS (defined as a primary EMS agency in a area populated with 50,000 or more people in the immediate proximity of a tertiary care PED)⁵⁶ and rural EMS (i.e. EMS agency not included within an urban area) with PedAMINES and with the conventional preparation method. In a GEE logistic regression model, an interaction between interventions and urban/rural EMS will be tested to investigate a potential modification of the efficacy of PedAMINES in rural area compared with urban area. Results will also be correlated to the EMS exposition (i.e. total number of emergency calls per year per EMS divided by the number of paramedics working in that EMS). Analyses of primary and secondary outcomes will be conducted in paramedics with more or less than 10 years of experience.

Means and standard deviations will be determined for stress and satisfaction scores (Likert scale) of individuals for each questionnaire item as well as for the UTAUT questionnaire and reported with descriptive statistics. Pearson correlations will be computed between the HR measures obtained with the watch and the scenario phases for each of the drugs and preparation methods used.

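### The main models adjust only for drug type, which in the linear TDP/TDD models adds nothing to the arm comparison; prespecifying baseline experience, already collected, could give a modest gain in precision

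*Combined protocol and SAP*

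**What the plan says.** Section 2.3.14.1 analyses the primary outcome with a mixed-effects logistic model and TDP/TDD with a mixed-effects linear model. Each has a random intercept for paramedic and one adjustment. For errors: "The model will be adjusted for the type of medication since the risk of error can vary across medications". For times: "The model will be adjusted for the type of medication since TDP and TDD can vary across medications". No other covariate is named.

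On baseline data, 2.3.5.1 says that on the day of participation "paramedics will complete a survey collecting data regarding their demographics, care training, and simulation and computer experience". Sections 2.3.5.1 and 2.3.7 differ on whether the app training comes before or after allocation and should be reconciled, but both put the questionnaire before it.

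Professional experience appears in the analysis plan only in 2.3.14.2: "Analyses of primary and secondary outcomes will be conducted in paramedics with more or less than 10 years of experience". Urban/rural setting and EMS exposure are likewise confined to additional analyses.

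**The concern.** The arm effect is a comparison between paramedics, so its precision depends on how much paramedics differ from one another. Drug type varies only within paramedics and is identical in both arms, so it cannot account for any of that variation. Variables that might account for some of it are recorded before allocation and then left out of the main models. Section 2.1 itself argues that unfamiliar tasks raise cognitive load and error, and that paramedics get little paediatric practice, so experience is a plausible predictor.

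At stake are somewhat wider intervals than necessary for the TDP and TDD differences and, less certainly, a little information in the primary model. Covariates chosen after the data are seen would be open to challenge, so any adjustment has to be named in advance.

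**Working it through.** **1. The plan's own figure.** Section 2.3.8 takes 60% errors in controls, 90% power and an "absolute difference of at least 30% in proportions of medication errors between intervention groups", and concludes: "With a two-sided risk alpha of 0.05, the needed sample size is 56 paramedics per arm of the study". With the pooled-variance formula and no continuity correction:

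n = [1.96·√(2×0.45×0.55) + 1.2816·√(0.6×0.4 + 0.3×0.7)]² / 0.30² = (1.379 + 0.860)² / 0.09 ≈ 55.7, so 56 per arm.

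This matches. Power is 90.2% at 56 per arm and 92% at the 60 recruited, with no covariate adjustment.

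**2. What drug type does in the linear model.** Inputs from the documents: 60 paramedics per arm, four drugs each, the same scenario for all, no missing data expected (2.3.14.3). The arm estimate is the difference between arm averages of paramedic means, and drug effects cancel from it. Write ρ for the within-paramedic correlation and set the total variance, apart from drug effects, to 1:

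Var(arm) = (2/60) × [ρ + (1−ρ)/4].

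Drug type does not enter. In 40 simulated trials (120 paramedics, four drugs, ρ = 0.4), the arm standard error was 0.1343 with and without drug type, and the estimates were identical to rounding. The equality of the fitted standard errors requires the estimated paramedic variance to stay above zero when drug type is omitted, which is one more reason to keep the term.

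**3. What a baseline covariate does.** If it explains a share R² of between-paramedic variance, the bracket becomes ρ(1−R²) + (1−ρ)/4. The documents give neither ρ nor R², so both are assumed:

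| ρ | No covariate | R² = 10% | SE ratio | R² = 20% | SE ratio |
|---|---|---|---|---|---|
| 0.3 | 0.475 | 0.445 | 0.968 | 0.415 | 0.935 |
| 0.5 | 0.625 | 0.575 | 0.959 | 0.525 | 0.917 |
| 0.7 | 0.775 | 0.705 | 0.954 | 0.635 | 0.905 |

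The standard error falls by about 3% to 10%. The equivalent gain in sample size runs from 0.475/0.445 − 1 = 7% to 0.775/0.635 − 1 = 22%.

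**4. The lower end.** Now let R² be the share of the variance of a paramedic's four-drug mean. At 2%, the SE ratio is √0.98 = 0.990; at 5%, 0.975. Three useless covariates cost a factor of about √(118/115) = 1.013, so the break-even R² is about 1 − 115/118 = 2.5%. Below about 3% there is almost nothing to gain.

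**5. If experience matters only in the control arm.** Assume it explains 20% of between-paramedic variance there and none with the app, with equal variances and ρ = 0.5. A common slope is then half the control-arm slope, and leaves 1 − 0.20 + 0.05 = 0.85 in controls and 1 + 0.05 = 1.05 with the app, an average of 0.95. The bracket becomes 0.5×0.95 + 0.125 = 0.600 against 0.625. The SE ratio is √0.96 = 0.980, a fall of 2%.

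**6. The logistic model.** Here drug type does change the fitted numbers. In 100 simulated trials (assumed random-intercept SD 1.2, arm log-odds ratio −0.7, covariate share 30%):

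| Model | SE of log-odds ratio | Mean absolute z |
|---|---|---|
| Arm only | 0.287 | 2.22 |
| Arm + drug type | 0.318 | 2.21 |
| Arm + drug type + covariate | 0.292 | 2.39 |

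Drug type rescales the log-odds ratio without adding information on the arms. With a 10% share (60 trials), the covariate moved the SE only from 0.317 to 0.306. With a log-odds ratio of −1.8 (error rates about 57% and 26% of preparations), all 100 trials were significant under every model.

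**The case against.** The planned comparison is randomised and unbiased, and its sample size reproduces without adjustment. The plan justifies the drug-type term by differences between drugs, which is legitimate; it never claims a gain in precision. All of this stands.

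The size of the gain is assumed. A simulation that builds in a given R² only recovers it, so it is not evidence that experience predicts performance here. Section 2.2 points the other way: it says the app's dose calculation does not depend on user competency and that delays were less spread with the app, which makes the 2% of step 5 credible. If EMS were also put in the model, experience might explain less of what remains.

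No main conclusion is likely to turn on this. Assume ρ = 0.5, R² = 20% and a total SD of about 100 s. In 60 simulated trials the standard error went from 14.37 s to 13.19 s, so the 95% half-width goes from 1.96×14.37 = 28 s to 1.96×13.19 = 26 s. The earlier in-hospital trial, as reported in the Summary and 2.2, found reductions of 141.8 to 170.5 s, and error rates 75.9 − 10.2 = 65.7 points apart.

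A reader might go further and infer that a chance imbalance in experience biases the result. With 60 per arm, a standardised covariate differs between arms with SD √(2/60) = 0.18, so about one trial in 20 exceeds 0.36. A valid interval already allows for that. What survives is the narrower point: a prespecified adjustment at small cost is not being used.

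**Conclusion.** The point holds as a possible loss of efficiency, most clearly for TDP and TDD. The unchanged standard error with drug type is established for the linear models with complete data; it should not be carried over to the logistic model, where the term changes both the estimate and its standard error.

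The gain ranges from practically nothing to roughly a tenth of the standard error, and the documents cannot say where in that range the trial lies.

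Three stronger readings are tempting and unsupported. The trial is not underpowered on this account, since 56 per arm stands without covariates. Precision is not shown to be lost for nothing, since R² may be close to zero. The drug-type term is not redundant: it describes drug differences and protects against unbalanced missing preparations. Priority is low.

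**What to change.** In 2.3.14.1, keep drug type and prespecify years of paramedic experience (continuous) as a fixed effect in the TDP and TDD linear mixed models. Optionally add the care-training item, coded as the pre-randomisation survey actually records it. The documents do not list years of experience as a survey item (it is implied by the 10-year split) and describe training only in general terms, so the sponsor should confirm both fields first.

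Use the same covariates in the primary logistic mixed model, and report the result without them beside it, because the adjusted odds ratio is conditional on the covariates.

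Two housekeeping lines are needed. Section 2.3.7 calls the demographic questionnaire anonymised, so link it to the performance data by study code. Section 2.3.14.3 prescribes complete-case analysis, so state that a paramedic with a blank covariate stays in the main analysis, for example through simple baseline imputation. The questionnaire check in 2.3.12.1 makes blanks unlikely but does not rule them out.

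The cost is a few sentences of analysis text and, if the fields are confirmed, no new data. If the covariates turn out useless, three of them would widen the standard error by about 1.3%, and one or two by less.
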